14.6. Secondary Analysis

Not applicable.

14.7. Other Exploratory Analysis

Exploratory hypotheses on distance binocular HLHC logMAR VA will be assessed using the same model as the primary analysis. Comparisons between EMO-114 and the other two study lenses will be conducted based on the 2-sided 95% CIs constructed for the mean differences between EMO-114 and EMO-118 (EMO-114 – EMO-118) and between EMO-114 and MiSight (EMO-114 – MiSight). Superiority of EMO-114 lens relative to EMO-118 lens will be declared if the upper bound of the 95% CI for the mean difference is less than 0. Superiority of EMO-114 lens relative to MiSight lens will be declared if the upper bound of the corresponding 95% CI is less than 0.

Patient-reported outcome (PRO) items will be used to measure subjective vision, comfort, and ease of handling, with descriptive summaries tabulated by lens type. Exploratory analysis will be conducted to evaluate the psychometric properties of these PRO measures.

Descriptive data summaries will be tabulated by lens type for all other exploratory endpoints. A by-subject listing of all adverse events (ocular and non-ocular AEs) will be provided.

As supplementary analyses to support the primary analysis, two sensitivity analyses may be considered. (1) If non-inferiority for the primary endpoint is met with subjects in the per-protocol population, a sensitivity analysis using ITT population may be considered. (2) To evaluate the impact of missing data, a sensitivity analysis using ITT population with missing data imputed may be conducted using multiple imputation methods if the proportion of subject dropout is greater than the 15%. The SAS/STAT procedures PROC MI and PROC MIANALYZE will be utilized with a parametric regression method using the fully conditional method (FCS) to make at least 50 imputations.²¹

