Another known risk is that the optical design of myopia control soft contact lenses may not provide equivalent vision quality to a conventional spherical lens design. While minimal difference has been measured between optical designs using high contrast visual acuity, reductions in low contrast and/or low luminance conditions have been reported.¹⁵ While the visual experience with a soft myopia control contact lens may be different, children using MiSight 1 Day have subjectively rated their overall vision similarly to a parallel control group using single vision spectacles after 12 and 24 months of wear.⁸ To manage this risk, the protocol is designed to ensure that each subject meets a minimum visual acuity and reports acceptable subjective vision prior to study contact lens dispense.

No additional risks associated with participation in this investigation are anticipated.

Clinical Study Protocol

Johnson & Johnson Vision Care, Inc.

For the most comprehensive risk and benefit information regarding the EMO lenses refer to the latest version of the Investigator's Brochure for EMO Design Family Lenses and the package insert of the marketed products.

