2. STUDY OBJECTIVES, ENDPOINTS AND HYPOTHESES

2.1. Objectives

Primary Objective

The primary objective is to evaluate the logMAR visual performance of soft contact lenses featuring myopia control optical designs.

Exploratory Objectives

The exploratory objectives of the study are to assess:

- logMAR visual performance at 4 m under varying luminance and contrast conditions
- logMAR visual performance at 40 cm under high and low contrast conditions
- Patient-reported outcomes at fitting and follow-up
- Assess safety through adverse events, slit lamp findings, and subject-reported ocular symptoms
- Number of power modifications and over-refraction with first trial lens at fitting

Clinical Study Protocol

Johnson & Johnson Vision Care, Inc.

- Over-refraction at follow-up
- Lens fitting characteristics

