2.3. Hypotheses

The primary hypothesis must be met to satisfy the objective of the study.

Primary Hypothesis

1. The distance (4 m) binocular high luminance high contrast visual acuity (in logMAR) with EMO-118 will be non-inferior to that of MiSight at follow-up visit. A non-inferiority margin of 0.05 logMAR will be used.

Clinical Study Protocol

Johnson & Johnson Vision Care, Inc.

Other Exploratory Hypotheses

1. The distance (4 m) binocular high luminance high contrast visual acuity (in logMAR) with EMO-114 will be superior to that of EMO-118 at follow-up visit.
2. The distance (4 m) binocular high luminance high contrast visual acuity (in logMAR) with EMO-114 will be superior to that of MiSight at follow-up visit.

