14.2. Sample Size Justification

The plan is to enroll approximately 75 eligible subjects with a minimum of 50 subjects targeted to compete the study. Given no historical data is available for the Control lens (MiSight 1 Day), a power analysis for the primary endpoint was conducted to estimate statistical power based on historical data for the Test lens (EMO-118) under various scenarios with different assumptions and sample sizes.

EMO-118 and EMO-114 lenses were evaluated in a historical study (████████) with a parallel group design. Table 7 below presents the descriptive statistics of distance binocular logMAR VA under bright HLHC at 1-week follow-up observed from ██████████

Table 7: Descriptive Summaries of Binocular LogMAR Visual Acuity at 1-week Follow-up from ██████████ – Per Protocol Subjects

	EMO-114	EMO-118
Number of subjects	42	41
Mean (SD)	-0.12 (0.083)	-0.08 (0.084)

SD = standard deviation

Considering different number of subjects to complete the study (i.e., 40, 50, or 60), a power analysis was conducted for the primary hypothesis based on the assumptions for correlation between repeated measures, standard deviation for the Control lens, and effect size (i.e., mean difference between the Test and the Control). It was assumed that the standard deviation of MiSight is the same EMO-118 with respect to distance binocular HLHC logMAR VA. Power was estimated using a paired sample *t*-test with a 2-sided type I error rate of 5% and non-inferiority margin of 0.05. The calculation was performed using the POWER procedure in SAS Version 9.4. Table 8 below shows the estimated statistical power under different scenarios. Given time and resource constraints, fifty subjects have been considered as the optimal number which demonstrated an acceptable level of statistical power under most assessed scenarios. Therefore, the plan is to enroll approximately 75 eligible subjects with a minimum of 50 subjects targeted to compete the study.

Clinical Study Protocol
Johnson & Johnson Vision Care, Inc.

Table 8: Power Analysis for the Primary Hypothesis

Endpoint	Standard Deviation	Mean Difference (EMO-118 - MiSight)	Correlation	Completed Subjects	Power
Distance Binocular HLHC LogMAR VA	0.084	0	0.3	40	87.3%
				50	93.7%
				60	96.9%
		0.01	0.5	40	95.6%
				50	98.5%
				60	99.5%
		0.01	0.3	40	69.9%
				50	79.7%
				60	86.6%
		0.01	0.5	40	83.6%
				50	91.0%
				60	95.2%

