14.4. Level of Statistical Significance

The planned primary analysis for this study will be conducted with a two-sided type I error rate of 5%. Each exploratory analysis will be conducted with a two-sided type I error rate of 5%.

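### Binocular low-contrast and low-luminance distance acuity get only by-lens descriptive tables, so the plan gives no between-lens difference with an interval for them and does not use the crossover pairing.

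*Combined protocol and SAP*

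**What the plan says.** Among the exploratory objectives, section 2.1 lists "logMAR visual performance at 4 m under varying luminance and contrast conditions". Section 2.2 lists binocular HLLC and LLHC acuity at 4 m as exploratory endpoints. Section 7.2 has both measured at each follow-up visit, in the same session as the primary measurement.

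Section 1.4, on known risks, compares myopia-control optics with a conventional spherical lens. It says high-contrast acuity has shown little difference between designs, while "reductions in low contrast and/or low luminance conditions have been reported".

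All three hypotheses in section 2.3 (one primary, two exploratory) concern binocular high-luminance high-contrast (HLHC) acuity at 4 m. For the primary one, "A non-inferiority margin of 0.05 logMAR will be used", and the section adds: "The primary hypothesis must be met to satisfy the objective of the study".

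Section 14.5 analyses HLHC with a linear mixed model and a 95% confidence interval. Section 14.6 has no secondary analysis. Section 14.7 applies the same model to the two EMO-114 hypotheses, again on HLHC, and then states: "Descriptive data summaries will be tabulated by lens type for all other exploratory endpoints". HLLC and LLHC fall under that sentence.

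**The concern.** Section 4.2 justifies the crossover by its removal of between-subject variability from lens comparisons. A table of n, mean, SD, median and range for each lens, which is the summary set in section 14.1, does not use that property. It gives no between-lens difference, no interval and no adjustment for period.

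The exploratory objective on varying luminance and contrast would therefore be answered without any statement of precision. Yet these are the two distance conditions that the risk section singles out. A reader asking how EMO-118 compares with MiSight in low contrast or dim light would have to subtract two means and guess at the uncertainty, although the data for a proper paired estimate will have been collected.

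**Working it through.** **Inputs.** From section 14.2: SD 0.084 for EMO-118 on binocular HLHC (Table 7); the same SD for MiSight ("It was assumed that the standard deviation of MiSight is the same EMO-118 with respect to distance binocular HLHC logMAR VA"); correlation 0.3 or 0.5; 50 completers; and a paired t-test "with a 2-sided type I error rate of 5% and non-inferiority margin of 0.05". The document gives no SD or correlation for HLLC or LLHC. The SDs of 0.084 to 0.15 used for them below are assumptions, and the correlations are borrowed from Table 8.

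**Step 1: reproduce the plan's own figures (HLHC).**
- SD of the paired difference = SD × √(2(1 − ρ)). At ρ = 0.3 this is 0.084 × √1.4 = 0.0994; at ρ = 0.5 it is 0.0840.
- SE with n = 50: 0.0994/√50 = 0.0141; 0.0840/√50 = 0.0119.
- Noncentrality = (0.05 − true difference)/SE, with 49 df and one-sided 2.5%.
- Power at true difference 0: 93.7% (ρ = 0.3) and 98.5% (ρ = 0.5). At 0.01: 79.7% and 91.0%.

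These equal the Table 8 entries, and all 12 cells of that table reproduce to within 0.1 percentage point. The HLHC power statement is sound, but it covers HLHC only.

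**Step 2: precision of a paired interval for HLLC or LLHC.** Half-width = t(0.975, 49 df) × SD × √(2(1 − ρ)/50).

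| Assumed SD | ρ = 0.3 | ρ = 0.5 |
|---|---|---|
| 0.084 | 0.0282 | 0.0239 |
| 0.10 | 0.0336 | 0.0284 |
| 0.12 | 0.0404 | 0.0341 |
| 0.15 | 0.0504 | 0.0426 |

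The protocol equates 0.20 logMAR with 10 letters, so one letter is 0.02 logMAR and the range is about 1.2 to 2.5 letters.

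**Step 3: precision from by-lens means and SDs alone.** Treating the lenses as independent groups, SE = 0.084 × √(2/50) = 0.0168 and the 95% half-width is 0.0333. Pairing shortens this by 1 − 0.0282/0.0333 = 15% at ρ = 0.3 and by 1 − 0.0239/0.0333 = 28% at ρ = 0.5. The absolute widths scale with the SD; the percentage gain does not.

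**Caveat.** Steps 2 and 3 use the simple paired and unpaired t forms, matching the plan's power method. The model in section 14.5 also carries period, sequence and first-order carryover terms. Adjusting for carryover would widen the intervals somewhat and could give back part of the gain in Step 3.

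**The case against.** Descriptive summaries for a long list of declared exploratory endpoints, with no hypotheses or margins, are a legitimate choice and avoid unadjusted intervals. The by-lens tables are also not empty. Among children with data on all three lenses, the difference of the by-lens means equals the mean paired difference, and with positive correlation the unpaired interval is conservative. This much stands: the loss is one of precision and of a stated interval, not of the whole comparison. It depends on the tables using the same children for every lens, and section 14.7 names no population for them. The tables also leave period unadjusted, and 50 completers cannot divide equally over six sequences.

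Section 14.1 defers detail to a stand-alone SAP that is not part of the document reviewed, and section 14.4 sets a two-sided 5% level for each exploratory analysis. Neither specifies a lens comparison for HLLC or LLHC, and the sentence in section 14.7 is explicit.

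A reader might infer more than the text allows:
- **That the protocol expects EMO-118 to lose acuity against MiSight in these conditions.** Section 1.4 compares with a conventional spherical lens. MiSight is itself a myopia-control lens, and its package insert in Appendix C warns of reduced image contrast, ghosting and halos in low light. No direction is predicted for this comparison.
- **That HLHC is the condition least able to separate these lenses.** Table 7 shows mean HLHC acuity of −0.12 for EMO-114 and −0.08 for EMO-118, a gap of 0.04. No HLLC or LLHC data are given for any study lens, so relative sensitivity cannot be judged.
- **That the primary claim covers visual performance in general.** The primary objective is worded broadly, but sections 2.3 and 14.5 already state the hypothesis and test as binocular HLHC acuity.
- **That a paired analysis would detect a 0.05 logMAR loss.** Power would be 93.7% to 98.5% at SD 0.084 but only 49.7% to 63.7% at SD 0.15, and the document does not say which is nearer.

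**Conclusion.** The point holds as a gap in the exploratory analysis. The plan sets an objective on acuity under varying luminance and contrast and collects binocular HLLC and LLHC acuity in a crossover, then gives no between-lens difference or interval for them. With 50 completers and correlation 0.3 to 0.5, a paired interval would have a half-width of about 0.024 to 0.028 logMAR at SD 0.084 (0.033 from by-lens summaries), or about 0.043 to 0.050 at SD 0.15. Either is informative as an exploratory estimate and needs no extra subjects. The figures rest on assumed SDs and borrowed correlations and ignore the extra model terms. The validity, error rate and decision rule of the primary HLHC test are unaffected.

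**What to change.** In section 14.7, take binocular HLLC and LLHC at 4 m out of the descriptive-only sentence. State that each will be analysed with the mixed model of section 14.5. Report the differences EMO-118 minus MiSight, EMO-114 minus EMO-118 and EMO-114 minus MiSight with two-sided 95% confidence intervals, beside the HLHC result. Label them exploratory, with no non-inferiority margin and no multiplicity claim, and name the analysis population. Carry the same text into the stand-alone SAP before database lock. Sections 2.3 and 14.5 need no rewording.

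The cost is a few sentences and two reruns of an existing model on data already being collected. The downside is 2 endpoints × 3 contrasts = 6 more unadjusted intervals, which should be read as estimates and not as tests.

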14.8. Interim Analysis

Not applicable.

14.9. Procedure for Handling Missing Data and Drop-Outs

Subject dropout is expected to be one of the main reasons of missing data in this clinical trial. Past clinical trials don't provide the evidence that subject dropout is systematic or not-at-random. Missing or spurious values will not be imputed. The count of missing values will be included in the summary tables and listings.

Clinical Study Protocol

Johnson & Johnson Vision Care, Inc.

14.10. Procedure for Reporting Deviations from Statistical Plan

The analysis will be conducted according to that specified in above sections. There are no known reasons for which it is planned to deviate from these analysis methods. If for any reason a change is made, the change will be documented in the study report along with a justification for the change.

15. DATA HANDLING AND RECORD KEEPING/ARCHIVING

15.1. Electronic Case Report Form/Data Collection

The data for this study will be captured on electronic case report forms (eCRFs) using the BioClinica EDC system. An authorized data originator will enter study data into the eCRFs using the EDC system. Data collected on equipment that is not captured in EDC will be formatted to the specification of the JJVC database manager and sent to JJVC for analysis.

External data sources for this study include: Not Applicable

The clinical data will be recorded on dedicated eCRFs specifically designed to match the study procedures for each visit. Only specifically delegated staff can enter data on a CRF. Once completed, the eCRFs will be reviewed for accuracy and completeness and signed by the Investigator. The sponsor or sponsor's representatives will be authorized to gain access to the subject recordation for the purposes of monitoring and auditing the study.

Edit checks, electronic queries, and audit trails are built into the system to ensure accurate and complete data collection. Data will be transmitted from the clinical site to a secure central database as forms are completed or updated, ensuring information accuracy, security, and confidentiality. After the final database lock, the Investigator will be provided with Individual Patient Profiles (IPP) including the full audit trail on electronic media in PDF format for all of the study data. The IPP must be retained in the study files as a certified copy of the source data for the study.

The content and structure of the eCRFs are compliant with ISO14155:2011.¹

15.2. Subject Record

At a minimum, subject record should be available for the following:

- subject identification
- eligibility
- study identification
- study discussion
- provision of and date of informed consent
- visit dates
- results of safety and efficacy parameters as required by the protocol
- a record of all adverse events
- follow-up of adverse events

Clinical Study Protocol

Johnson & Johnson Vision Care, Inc.

- medical history and concomitant medication
- test article receipt/dispensing/return records
- date of study completion
- reason for early discontinuation of test article or withdrawal from the study, if applicable

The subject record is the eCRF or an external record. The author of an entry in the subject record must be identifiable. The first point of entry is considered to be the source record.

Adverse event notes must be reviewed and initialed by the Investigator.

15.3. Trial Registration on ClinicalTrials.gov

This study will be registered on ClinicalTrials.gov by the Sponsor because this study is in the confirmatory clinical trial phase.

16. DATA MANAGEMENT

16.1. Access to Source Data/Document

The Investigator/Institution will permit trial-related monitoring, audits, IEC/IRB review and regulatory inspection(s) by providing direct access to source data/documents. Should the clinical site be contacted for an audit by an IEC/IRB or regulatory authority, JJVC must be contacted and notified in writing within 24 hours.

16.2. Confidentiality of Information

Information concerning the investigational product and patent application processes, scientific data or other pertinent information is confidential and remains the property of JJVC. The Investigator may use this information for the purposes of the study only. It is understood by the Investigator that JJVC will use information developed in this clinical study in connection with the development of the investigational product and therefore may disclose it as required to other clinical investigators and to regulatory agencies. In order to allow the use of the information derived from this clinical study, the Investigator understands that he/she has an obligation to provide complete test results and all data developed during this study to the Sponsor.

16.3. Data Quality Assurance

Steps will be taken to ensure the accuracy and reliability of data, include the selection of qualified investigators and appropriate clinical sites and review of protocol procedures with the Principal Investigator. The Principal Investigator, in turn, must ensure that all Sub-Investigators and clinical site personnel are familiar with the protocol and all study-specific procedures and have appropriate knowledge of the study article.

Clinical Study Protocol

Johnson & Johnson Vision Care, Inc.

Training on case report form completion will be provided to clinical site personnel before the start of the study. The Sponsor will review case report forms for accuracy and completeness remotely during the conduct of the study, during monitoring visits, and after transmission to data management. Any data discrepancies will be resolved with the Investigator or designee, as appropriate.

Quality Assurance representatives from JJVC may visit clinical sites to review data produced during the study and to assess compliance with applicable regulations pertaining to the conduct of clinical trials. The clinical sites will provide direct access to study-related source data/documents and reports for the purpose of monitoring and auditing by JJVC and for inspection by local and regulatory authorities.

16.4. Data Monitoring Committee (DMC)

Not applicable.

17. CLINICAL MONITORING

The study monitors will maintain close contact with the Principal Investigator and the Investigator's designated clinical site personnel. The monitor's responsibilities will include:

- Ensuring that the investigation is being conducted according to the protocol, any subsequent versions, and regulatory requirements are maintained.
- Ensuring the rights and wellbeing of subjects are protected.
- Ensuring adequate resources, including facilities, laboratories, equipment, and qualified clinical site personnel.
- Ensuring that protocol deviations are documented with corrective action plans, as applicable.
- Ensuring that the clinical site has sufficient test article and supplies.
- Clarifying questions regarding the study.
- Resolving study issues or problems that may arise.
- Reviewing of study records and source documentation verification in accordance with the monitoring plan.

18. ETHICAL AND REGULATORY ASPECTS

18.1. Study-Specific Design Considerations

Potential subjects and their parents/legal guardians will be fully informed of the risks and requirements of the study and, during the study, subjects and their parents/legal guardians will be given any new information that may affect their decision to continue participation. Subjects and their parents/legal guardians will be told that their consent to participate in the study is voluntary and may be withdrawn at any time with no reason given and without penalty or loss of benefits to which they would otherwise be entitled. Subjects will only be enrolled if the subject's parents/legal guardians are fully able to understand the risks, benefits, and potential adverse events of the study and provide their consent voluntarily, and, the subject provides their assent voluntarily.

Clinical Study Protocol

Johnson & Johnson Vision Care, Inc.

18.2. Investigator Responsibility

The Principal Investigator is responsible for ensuring that the clinical study is performed in accordance with the signed agreement, the investigational plan, section 4 of the ICH E6(R2) guidelines on Good Clinical Practice (GCP),² and applicable regulatory requirements. GCP is an international ethical and scientific quality standard for designing, conducting, recording, and reporting studies that involve the participation of human subjects. Compliance with this standard provides public assurance that the rights, safety, and well-being of study subjects are protected, consistent with the principles of the Declaration of Helsinki 64th WMA General Assembly 2013³ and that the clinical study data are credible. The Investigator must maintain clinical study files in accordance with section 8 of the ICH E6(R2) guidelines on Good Clinical Practice (GCP),² and applicable regulatory requirements.

